8.1 Institutional Review Boards

All sites will submit the study protocol, informed consent form, and other study documents to their IRB for approval—the approval letter for each clinical center will be stored. Any amendments to the protocol, other than minor administrative changes, must be approved by each IRB before they are implemented.

8.2 Adverse Events

An adverse event (AE) is any untoward medical occurrence associated with the use of a drug in a subject whether or not considered drug or biologic related. An AE can therefore be any unfavorable and unintended sign, symptom or disease temporally associated with the use of a pharmaceutical product or biologic.

8.3 Suspected Adverse Reaction

A suspected adverse reaction (SAR) is any adverse event for which there is a reasonable possibility that the drug caused the event. “Reasonable possibility” suggests there is a causal relationship between the drug and the adverse event. “Suspected adverse reaction” implies a lesser degree of certainty about causality than adverse reaction, which means any adverse event caused by a drug.

8.4 Serious Adverse Events

An AE or SAR is considered serious if the Investigator or sponsor believes any of the following outcomes may occur:

- Death
- Life-threatening AE: Places the subject at immediate risk of death at the time of the event as it occurred. It does not include an AE that, had it occurred in a more severe form, might have caused death.
- Persistent or significant incapacity or substantial disruption of the ability to conduct normal life functions.
- Inpatient hospitalization or prolongation of hospitalization.
- Congenital anomaly or birth defect.
- Important medical events that may not result in death, be life threatening, or require hospitalization may be considered a serious adverse event when, based upon appropriate medical judgment, they may jeopardize the subject and may require medical or surgical intervention to prevent one of the outcomes listed in this definition above.

This determination is based on the opinion of either the investigator or sponsor (e.g., if either believes it is serious, it must be considered serious).

8.5 Laboratory Test Abnormalities

For laboratory test abnormalities that meet the definition of a serious adverse event (SAE), which required the subject to have the study drug discontinued or interrupted, or required the subject to receive specific corrective therapy, the clinical diagnosis rather than the laboratory term will be used by the reporting investigator (e.g., anemia versus low hemoglobin value).

8.6 Assessment of Causal Relationship and Severity

A medically-qualified investigator must assess the relationship of any AE to the use of study drug, based on available information, using the following guidelines:

- **Not related:** There is not a reasonable causal relationship to the investigational product and the adverse event.
- **Unlikely related:** No temporal association or the cause of the event has been identified, or the drug or biologic cannot be implicated.
- **Possibly related:** There is reasonable evidence to suggest a causal relationship between the drug and adverse event.
- **Related:** There is evidence to suggest a causal relationship, and the influence of other factors is unlikely.

The determination of adverse event severity rests on medical judgment of a medically-qualified Investigator. The severity of AEs will be graded using the following definitions:

- **Mild:** Awareness of sign, symptom, or event, but easily tolerated;
- **Moderate:** Discomfort enough to cause interference with usual activity and may warrant intervention;
- **Severe:** Incapacitating with inability to do usual activities or significantly affects clinical status, and warrants intervention.

8.7 Expectedness

The expectedness of an AE or SAR shall be determined according to the specified reference document containing safety information (e.g., most current product label). Any AE that is not identified in nature, severity, or specificity in the current study drug reference document(s) is considered unexpected. Events that are mentioned in the product label as occurring with a class

of drugs or as anticipated from the pharmacological properties of the drug, but not specifically mentioned as occurring with the particular drug under investigation are considered unexpected.

Anticipated Adverse Events and Procedure Effects

The following are anticipated, disease-related events in patients with HF or anticipated events of interest in patients with HFpEF taking Entresto™:

- **Arrhythmias:** This refers to both atrial and ventricular arrhythmias.
- **Acute coronary syndrome:** This refers to unstable angina, non ST segment elevation myocardial infarction (NSTEMI), and ST segment elevation myocardial (STEMI).
- **Unplanned hospitalization, ER visit or clinic visit for worsening HF:** This refers to treatment for acute heart failure such as receiving intravenous diuretics.
- **Cerebrovascular event:** This refers to cerebrovascular accidents (stroke) of any cause (hemorrhagic, ischemic, or embolic) and transient ischemic attack (TIA).
- **Venous thromboembolism:** This includes both deep venous thrombosis and pulmonary embolus.
- **Worsening renal function:** This refers to acute kidney injury, typically defined as an increase in eGFR \geq 20% over 48 hours, or progressive loss of renal function over time.
- **LVAD implantation:** This refers to implantation of a temporary or durable LVAD.
- **Cardiac Transplantation**
- **Hyperkalemia > 6 mEq/L**
- **Acute renal failure with serum creatinine > 2.5 mg/dL**
- **Angioedema**
- **Symptomatic hypotension**

Anticipated disease related events will not be captured as AEs/SAEs during the study, but will be entered on the appropriate case report form ("Events of Interest" page).

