4.2 Exclusion Criteria

1. History of hypersensitivity or allergy to ACE inhibitors (ACEIs), ARBs, or NEP inhibitors
2. Known history of angioedema to ACE inhibitors (ACEIs) or ARBs
3. Previous LVEF < 40% at any time
4. Systolic blood pressure < 100 mmHg or > 180 mmHg
5. Current acute decompensated HF (exacerbation of chronic HF manifested by signs and symptoms that may require intravenous therapy)
6. Unstable angina, myocardial infarction, stroke, transient ischemic attack, or cardiovascular surgery or urgent percutaneous coronary intervention (PCI) within 3 months of screening or elective PCI within 30 days of entry
7. Significant valvular stenosis or regurgitation (greater than moderate in severity), hypertrophic, restrictive or obstructive cardiomyopathy including amyloidosis, constrictive pericarditis, primary pulmonary hypertension, or biopsy proven active myocarditis
8. Severe congenital heart disease
9. History of heart transplant or with LV assist device
10. Evidence of severe hepatic disease as determined by any one of the following: history of hepatic encephalopathy, history of esophageal varices, or history of porto-caval shunt.
11. Glomerular filtration rate < 20 ml/min/1.73 m² on most recent clinical laboratories*
12. Serum potassium of > 5.5 mEq/dL on most recent clinical laboratories*
13. Concomitant use of aliskiren in patients with diabetes
14. Currently receiving an investigational drug
15. Inability to comply with planned study procedures

- 16. Female subject who is pregnant or breastfeeding
- * Performed within 90 days of enrollment

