6.1 Screening Visit

Possible study participants will meet with study coordinator to review consent form. Medical history and current medications will be reviewed. Blood will be drawn for baseline serum NEP levels, safety laboratory tests (potassium, creatinine) and pregnancy test if necessary at the CRTU. Dependent on the results of the NEP levels which will be available within 48 hours, subjects will be assigned to a high or low NEP group. If subjects are found to be eligible and are on ACEi or ARBs, subjects will be instructed to withhold these drugs 36 hours before the initiation of treatment with Entresto™ at Visit 1 and throughout the duration of the study while subjects are on Entresto™.

6.2 Visit 1

Visit 1 will occur within 30 days of the Screening Visit. Qualified subjects will be evaluated as outpatients at the CRTU. Interim history, a review of medications, NYHA class assessment and a brief physical exam will be performed by a qualified study team member. Blood will be drawn for serum NEP levels, NT-proANP, NT-proBNP, NT-proCNP, cGMP and a pregnancy test will be performed, if necessary; urine sample will also be collected for cGMP levels. An additional 55 mL blood sample will be collected from subjects, for future transcriptomic, metabolomic and genomic analysis, who provide consent to allow their blood to be stored in the BAP laboratory for future studies. Subjects will be given the option to opt in or out of this component of the study. Following this, subjects will receive their first dose of Entresto™. BPs will be monitored at baseline prior to

administration of Entresto™ and 60 minutes after this first dose to ensure tolerance of the medication. Sitting systolic and diastolic BP will be monitored in the subject's dominant arm 3 times with an automatic blood-pressure monitor (Omron, Bannockburn, IL) and an average reading of these 3 measurements will be used. Before dismissal, subjects will be provided with Entresto™ tablets for the duration of the study. Study coordinator will follow-up with the subject by telephone on day 14 ± 5 post-visit 1 to monitor compliance and to assess tolerance.

6.3 Visit 2

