8.8 Recording and Reporting of Adverse Events

The site Investigator is responsible for monitoring the safety of participants enrolled into the study at the study sites. For this study, non-serious AEs will not be collected on the safety reporting page of the CRF, but should be documented in the source documents and followed according to local standard of care.

SAEs, except for those anticipated AEs listed above, occurring from *signed informed consent* to Week 5 visit will be captured on the SAE CRF. Unless exempted as described above, all SAEs, whether or not deemed drug-related or expected, must be reported by the investigator or qualified designee within 1 working day of first becoming aware of the event. The investigator or qualified designee will enter the required information regarding the SAE into the appropriate CRF, which will be distributed to the appropriate sponsor contact.

Information collected on the adverse event worksheet (and entered in the research database):

- Subject's name:
- Medical record number:
- Disease/histology (if applicable):
- The date the adverse event occurred:
- Description of the adverse event:
- Relationship of the adverse event to the research (drug, procedure, or intervention):
- If the adverse event was expected:
- The severity of the adverse event: (use a table to define severity scale 1-5)
- If any intervention was necessary:

- Resolution: (was the incident resolved spontaneously, or after discontinuing treatment)
- Date of Resolution

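### The definition of worsening renal function runs against its own name, and the potassium exclusion is in a different unit from the hyperkalemia event

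*Combined protocol and SAP*

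**What the plan says.** Section 8.7 (Expectedness) lists events anticipated in this population or with this drug. Three entries matter here:

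- Worsening renal function is equated with acute kidney injury, "typically defined as an increase in eGFR" of at least 20% over 48 hours, "or progressive loss of renal function over time".
- "Hyperkalemia > 6 mEq/L".
- "Acute renal failure with serum creatinine > 2.5 mg/dL".

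The list has a function. Section 8.7 closes with "Anticipated disease related events will not be captured as AEs/SAEs during the study" and sends these events to an Events of Interest page. Section 8.8 repeats the exemption: what goes on the SAE form is "SAEs, except for those anticipated AEs listed above", and the one-working-day reporting duty applies only to events that are not exempt.

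In Section 4.2, exclusion 12 reads "Serum potassium of > 5.5 mEq/dL on most recent clinical laboratories". A footnote requires that result to be no more than 90 days old at enrollment.

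**The concern.** A rise in eGFR means better filtration, so the numeric part of the definition describes the reverse of the event it is meant to define. Because the list governs which events skip the SAE form and its reporting clock, the wording is a rule and not just background.

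The potassium limit is an eligibility rule. The protocol uses two units for the same analyte, a factor of ten apart, and the one in the exclusion criterion gives a limit that cannot screen anyone out.

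If either text were followed to the letter, an event could be classified against the sense of its own heading, or a subject could be admitted whom the criterion was plainly written to consider.

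**Working it through.** The plan states no derived figure to reproduce on this point. The check is a side-by-side reading, one unit conversion and a look at the test schedule.

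**1. Direction of eGFR (Section 8.7).**
- Name of the entry: worsening of renal function.
- Numeric limb: a rise of at least 20% in 48 hours.
- Second limb: a progressive loss.

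Take an illustrative starting eGFR of 60 (an assumption; the documents give no example). A 20% rise gives 60 × 1.20 = 72, which meets the numeric limb. A 20% fall gives 60 × 0.80 = 48, which does not. The name and the second limb point one way and the numeric limb points the other, so the entry contradicts itself.

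**2. Potassium unit (Section 4.2 against Section 8.7).**
- Exclusion limit as written: 5.5 mEq/dL.
- Event threshold as written: 6 mEq/L.
- Conversion: 1 L = 10 dL, so 5.5 mEq/dL × 10 dL/L = 55 mEq/L.
- Ratio to the event threshold: 55 / 6 = 9.17, about 9.2.

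An entry limit some nine times the level that the protocol itself treats as a hyperkalemia event would exclude nobody.

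**3. Test schedule (for the optional note only).**
- Screening: Section 6.1 draws "safety laboratory tests (potassium, creatinine") along with NEP. Note a to the Schedule of Events Table makes this conditional on need, which Section 6.1 does not.
- Visit 1: biomarkers, optional stored blood and, where needed, a pregnancy test, all before the first dose (Section 6.2).
- Around day 14: a telephone contact.
- Visit 2: biomarkers and optional stored blood (Section 6.3 and note b to the table).

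Scheduled potassium or creatinine values after the first dose: none. This is a fact about the schedule. Whether it amounts to an error is taken up under the objection.

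**The case against.** **Both are drafting slips that nobody would apply literally.** This is largely right. The renal entry names acute kidney injury before it gives the eGFR wording, which is introduced as a typical definition. A true fall in kidney function would still reach the list through that name, through the second limb or, above 2.5 mg/dL, through the separate creatinine entry. No particular event can be shown to be misrouted. On potassium, a reader of a laboratory report would not take 55 mEq/L as the intended limit. The objection settles the severity. It does not remove the contradictions, because both sentences are rules that fail if followed as written.

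**A stronger reading is tempting.** A reader might infer that the potassium- and creatinine-defined events conflict with a schedule that has no on-treatment test, so that the plan must be reconciled there too and a zero count could not be told apart from not testing. The documents do not support this, for four reasons:

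- Section 8.7 says which events are anticipated and where to record them. It does not promise to test for them. The same list includes arrhythmias and venous thromboembolism, for which the schedule lists no dedicated test either.
- There are other routes of ascertainment: source documents and local standard of care (Section 8.8), a site data and safety-monitoring plan (Section 8.10), laboratory and follow-up forms (Section 9.3) and chart extraction (Section 9.4). Section 9.3 also requires missing data to be explained and procedures not done to be marked N/D. The forms and the site plan are not in these documents, so one cannot say that they fail to identify untested subjects.
- Statistical Methods (Section 7.2) analyses no safety rate.
- Section 8.10 already says that the study does not give definitive safety information.

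One can compute how an upper confidence bound for zero events widens as fewer of the 40 subjects are tested. The number tested would have to be assumed, and the result would not measure any error in the plan.

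**Conclusion.** Two operative texts are wrong as written. The eGFR direction in Section 8.7 contradicts the rest of its own entry. The potassium unit in exclusion 12 differs by a factor of ten from the unit in Section 8.7, so that the literal limit is 55 mEq/L. Both conclusions come from the text and a unit conversion, and the only assumption is the illustrative eGFR of 60.

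Severity is minor. Literal misapplication is unlikely, no misrouted event or wrongly admitted subject can be pointed to, and the biomarker comparison is unaffected.

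The lack of a scheduled on-treatment potassium or creatinine value is not an error in the plan. It matters only if these Events of Interest are later presented as rates. In that case 40 would not necessarily be the number in whom the event could have been detected.

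**What to change.** 1. In Section 8.7, reconcile the direction of the eGFR change with the entry's name and second limb.
2. Reconcile the potassium unit in exclusion 12 (Section 4.2) with the unit used in Section 8.7.

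Which wording and limit are intended is for the sponsor to confirm; none is proposed here. The cost is a short text amendment, with no added test, visit or analysis.

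Optional, and only if the potassium- and creatinine-defined events are reported as rates: give the number of subjects with at least one on-treatment value of each analyte, and state that ascertainment was through usual care. This may cost more than one extra count, since finding tested but event-free subjects can require a search of each subject's records.

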8.2.8 Suspected Unexpected Serious Adverse Reaction

AEs that meet the criteria of serious, related to study drug, and unexpected for that drug, qualify for expedited reporting to the regulatory authorities. The Site Investigator will assess all SAEs occurring at his/her site and evaluate for “unexpectedness” and relationship to study drug. The Site Investigator is required to complete and submit a voluntary MedWatch Report for the events identified as serious, study drug related and unexpected at:

<https://www.accessdata.fda.gov/scripts/medwatch/>. A copy of this report should be kept at the site and also forwarded to the overall study PI within the same timeline used for reporting to regulatory authorities.

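### Sections 8.7 and 8.8 exempt listed events from SAE capture and the 1-working-day report with no exception for drug-related cases, and this is not reconciled with 8.6, 8.2.8 or the label-based expectedness rule

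*Combined protocol and SAP*

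**What the plan says.** Section 8.7 does three things that bear on this point.

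- It sets expectedness by the reference safety document, for example the current product label: "Any AE that is not identified in nature, severity, or specificity in the current study drug reference document(s) is considered unexpected".
- It gives a list of twelve items, introduced as "The following are anticipated, disease-related events in patients with HF or anticipated events of interest in patients with HFpEF taking" Entresto. Several items are broad. For arrhythmias, "This refers to both atrial and ventricular arrhythmias". For cerebrovascular events, "This refers to cerebrovascular accidents (stroke) of any cause". For venous thromboembolism, "This includes both deep venous thrombosis and pulmonary embolus".
- It closes with the exemption: "Anticipated disease related events will not be captured as AEs/SAEs during the study". These events are entered on the Events of Interest page of the CRF.

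Section 8.8 excludes the anticipated events listed above it from the SAE CRF. It then sets the 1-working-day rule: "Unless exempted as described above, all SAEs, whether or not deemed drug-related or expected, must be reported".

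Section 8.2.8, printed after 8.8, makes serious, drug-related and unexpected events subject to expedited reporting to the authorities. It places the check on the site: "The Site Investigator will assess all SAEs occurring at his/her site". It does not repeat the exemption. Section 8.6 requires a causality assessment of any AE, also without an exemption.

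**The concern.** The exemption turns on whether an event is on the list. Neither 8.7 nor 8.8 brings an event back into SAE capture when the investigator thinks the drug caused it. Being anticipated in this disease and being expected for this drug are different properties, and 8.7 uses both without saying how they interact. A listed event can be anticipated, and so exempt, while also being unexpected against the label, and so a candidate for expedited reporting.

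What is at stake is the prompt recognition of a serious drug reaction. The study has a single arm (3.1), so event rates cannot be compared with a control. Use in HFpEF is off label (1.3). No DSMB was engaged, and medical monitoring consists of a regular look at the number and type of SAEs (8.10). Events that are not captured as SAEs can drop out of that look. In this setting, judgement on individual cases carries much of the weight.

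**Working it through.** No arithmetic applies. The check is to follow one event through the rules. Take a ventricular arrhythmia that leads to hospital admission, is judged related to study drug, and is not in the label. The last condition is an assumption, because the label is not part of the documents.

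1. **Definition (8.2, 8.4).** It is an AE, and serious because of the admission. Neither section has a carve-out.
2. **Causality (8.6).** An assessment is required for any AE. There is no carve-out here either.
3. **Expectedness (8.7, label rule).** It is unexpected, given the assumption.
4. **Exemption (8.7, closing sentence).** Arrhythmia is on the list without limit by cause, so the event goes on the Events of Interest page. The sentence is confined to disease-related events, so one can argue that a drug-caused arrhythmia falls outside it. The text does not say so.
5. **SAE CRF and 1-working-day report (8.8).** This exclusion covers everything listed, without the disease-related qualifier. In "Unless exempted as described above, all SAEs, whether or not deemed drug-related or expected, must be reported" the exemption comes first, so it overrides relatedness and expectedness. The event is off the SAE CRF and has no 1-working-day report.
6. **Expedited-reporting check (8.2.8).** There are two readings. If SAE has its 8.4 meaning, the site investigator must assess the event and file the MedWatch report. If SAE means an event captured as an SAE, the event drops out here. The text does not choose between them.
7. **What remains.** The Events of Interest page records the event, but no causality field, expectedness field or deadline is stated for it. The death and hospitalization forms in 9.3 record circumstances and details; no causality step or deadline is stated. The adverse event worksheet in 8.8 has relationship and expectedness items, but it is not said to apply to listed events. IRB reporting in 8.2.7 depends on the event counting as an AE.

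A second trace shows the difference in scope between 8.7 and 8.8. Angioedema and symptomatic hypotension are on the list, and 7.1 describes both as risks of the drug. Under the closing sentence of 8.7 they are arguably not disease related, hence not exempt. Under 8.8 they are listed, hence exempt. The two sections give different answers for the same event.

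**The case against.** The strongest reply is that 8.7 is a recording rule, not a definition. It says which CRF page is used and does not say that a listed event is no longer an AE or SAE. On the defined terms, 8.6 still requires causality, and 8.2.8 still covers every SAE at the site and is not tied to the SAE CRF. Anticipated decides the form and unexpected decides expedited reporting, so the two can coexist. Exempting common disease events from routine SAE capture is also a reasonable choice in a heart failure population.

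Much of this stands. A reader might infer that a drug-related listed event never reaches the expedited-reporting check. The documents do not support that, because 8.2.8 contains no exemption and loss from the check is only one of two readings. A reader might also infer that fatal events are exempt. Death is not one of the twelve items; it is a seriousness criterion in 8.4, and 9.3 provides for death forms. Nor can one conclude that a listed event is unexpected because 7.1 does not name it: 7.1 gives only reactions at 5% or more plus angioedema, and it is not the label.

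The reply does not reach 8.8. There the listed events leave the SAE CRF and the 1-working-day report in terms, whether or not they are drug-related. Nor does the disease-related qualifier in 8.7 close the gap: applying it takes a causality judgement, and the page on which these events are entered has no stated place for one.

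**Conclusion.** The point holds as a gap in the safety-reporting text. As written, 8.8 removes prompt SAE reporting from a serious listed event even when it is judged drug-related, and its exemption is wider than the one in 8.7. Whether such an event also misses the 8.2.8 assessment depends on how SAE is read there, and two investigators could follow the text and act differently.

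The scope is all twelve listed items under 8.8, and a smaller, undefined subset under 8.7. No frequency can be given, since the documents state no expected event rates. The part that concerns expedited reporting rests on the assumption that some listed events are not in the label. The loss of the SAE CRF entry and the 1-working-day report does not depend on that assumption. The point leaves the endpoints, the sample size and the analysis untouched. It should be corrected because it affects patient safety and is cheap to put right.

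**What to change.** - **8.7 and 8.8:** state in both, in the same words, that the exemption applies only to listed events the investigator judges not related or unlikely related to study drug on the 8.6 scale. Any serious listed event judged possibly related or related is recorded on the SAE CRF, reported within 1 working day and assessed under 8.2.8.
- **Events of Interest page:** add the 8.6 causality field, so that the judgement on which the exemption depends is recorded for each event.
- **8.2.8:** state that SAE has its 8.4 meaning and includes listed events.

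Wording the exemption identically in 8.7 and 8.8 also removes the difference in scope between them. The cost is a sentence in each of three sections, one extra CRF field and possibly some additional SAE forms. Sending every fatal listed event to the SAE CRF regardless of relatedness would be a further option, but this point does not require it.
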